6.3.2. Criteria for discontinuation of Investigational Product

Administration of the Investigational Product should be immediately discontinued in case the patient develops renal or hepatic dysfunction defined as:

renal dysfunction: the occurrence of both CL_{cr} < 60 mL/min and urine output < 0.5 mL/kg/hour on two consecutive sampling time points (12, 24, 36 hours after the beginning of Investigational Product infusion).

hepatic dysfunction: bilirubin exceeding 3 mg/dL and/or transaminases >3X upper limit of normal).

Phase 1 studies in patients with ESRD have shown that renal function has a profound effect on plasma concentrations of a major, marginally active metabolite, carboxy-repertaxin (DF2243Y), which was found to accumulate over time along with the increased elimination half-life. Even if toxicological results to date suggest that DF2243Y does not raise any safety concern, limited experience in humans recommends to discontinue the drug in case of renal impairment as it would not be possible to predict the risk associated with elevated plasma levels. However, transient alterations of serum creatinine or urine output, as defined above, do not indicate a renal dysfunction that would cause impaired excretion of DF2243Y. Because repertaxin undergoes extensive hepatic metabolism, it is also recommended that the infusion is discontinued in case of hepatic dysfunction to avoid an increase of plasma level of repertaxin, exceeding the target and safe concentration.

CL_{cr}, urine output, bilirubin and transaminases will be evaluated at 12, 24 and 36 hours after the beginning of Investigational Product infusion. Samples will be processed immediately and results made available as soon as possible to the Investigator. Urine output will be calculated for each of the 12 hour periods: from start of infusion to 12 hours, 12-24 hours, and 24-36 hours.

Investigational Product will also be immediately discontinued in the event of any other possibly drug related occurrences that the Investigator believes might compromise patient safety.

If the Investigational Product therapy is prematurely discontinued the primary reason for discontinuation must be recorded in the CRF. Patients who discontinue the treatment with the Investigational Product will not be withdrawn from the study by default, but will complete observations as per the protocol, unless otherwise withdrawn at the Investigator's decision.

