- A BAL will be performed during mechanical ventilation, in the interval between 12 and 24 hours after reperfusion, unless the patient is suffering from any clinical conditions which would be worsened by BAL procedures, in the opinion of the Investigator (see Appendix 1 for methodological details). Date and time of sampling will be recorded in the CRF along with location of BAL (lung, site) number of aliquots injected, amount recovered and summary of the most recent chest X-rays report. Specific reasons (hemodynamic instability, severe hypoxemia, etc.) for the decision to omit the BAL should be recorded in the CRF.

Renal (CLcr, urine output) and hepatic (bilirubin, transaminases) function will be tested at 12, 24, and 36 hours after the beginning of Investigation Product infusion.

Other clinical findings, including bronchoscopic and/or BAL findings, reports for all routine chest X-rays and thoracic CT scans, and results of routine biopsy will be copied into the CRF from the medical charts. AEs will be also recorded.

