### 9.6.4 Laboratory data

Samples for safety laboratory tests for hematology, clinical chemistry and coagulation are taken at Screening and hospital discharge. The following parameters will be included in the summary data presentations:

Hematology: hematocrit, hemoglobin, red blood cells, white blood cells, neutrophils, lymphocytes, monocytes, eosinophils, basophils

Clinical chemistry: sodium, potassium, chloride, bicarbonate, blood urea nitrogen (BUN), total bilirubin, alanine aminotransferase (ALT), aspartate aminotransferase (AST), serum creatinine

Coagulation: activated partial thromboplastin time (APTT), prothrombin time (PT), INR

Note: patients will either have a value for PT or INR at each time point.

Results for each parameter at screening and hospital discharge will be assessed as being below the lower limit of the normal range, within the normal range or above the upper limit of the normal range. The number and percentage of patients with out-of-range results and the number and percentage of patients with clinically significant out-of-range results will be presented for each parameter at each time point, together with the number of patients with results for that parameter and time point. Shifts in laboratory parameters during the hospital stay will also be presented for each parameter.

Creatinine clearance is calculated using Cockcroft-Gault formula at Screening and at 12, 24 and 36 hours post ICU admission for the assessment of renal and hepatic function during the study.

These data are used for assessment of patient during the study conduct phase and will be listed only.

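### The SAP plans no by-arm table of the renal and hepatic tests taken during the infusion, and it times them from ICU admission instead of infusion start

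*SAP*

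**What the plan says.** **Protocol.** After naming creatinine clearance (CLcr) and urine output, section 6.3.2 says that "bilirubin and transaminases will be evaluated at 12, 24 and 36 hours after the beginning of Investigational Product infusion". It adds: "Urine output will be calculated for each of the 12 hour periods". Section 7.5.2 repeats the schedule: "function will be tested at 12, 24, and 36 hours after the beginning of Investigation Product infusion". Section 2.4.3.4, Appendix 4 (footnote 2) and Appendix 6 use the same time origin; Appendix 6 allows ±4 h.

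The results feed a stopping rule in section 6.3.2:
- Renal: CLcr below 60 mL/min together with "urine output < 0.5 mL/kg/hour on two consecutive sampling time points".
- Hepatic: bilirubin above 3 mg/dL, or transaminases above three times the upper limit of normal, or both. No repeat is required.

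For renal impairment the stated reason is that "it would not be possible to predict the risk associated with elevated plasma levels".

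The laboratory safety endpoint (section 4.2.4) is the standard panel at screening and hospital discharge. Section 9.4.6 plans shift tables between those two points.

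**SAP.** Section 9.6.4 says CLcr is calculated at screening and "at 12, 24 and 36 hours post ICU admission", and then: "These data are used for assessment of patient during the study conduct phase and will be listed only". In section 11 the laboratory tables (3.3.1.1 to 3.3.2.3) cover the screening and discharge panel. The tests at 12, 24 and 36 h appear only in Listings 4.15.4 and 4.15.5. Section 9.4 leaves renal and hepatic function out of the baseline tables. Section 1.2 declares no changes from the protocol.

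**The concern.** Safety in this clinical setting is a stated objective. PK samples and blood gases aside, these are the only laboratory tests scheduled while the drug is running. The two tabulated time points, screening and discharge, both fall outside the infusion. A rise in bilirubin or a fall in CLcr that appears at 24 h and has resolved by discharge would leave the shift tables unchanged.

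The SAP is also uneven. Section 9.4 omits vital signs and renal and hepatic function from the baseline tables for the same reason: they are measured again later. Vital signs are then summarized by arm every 12 h (section 9.6.6). CLcr and urine output are never summarized, not even at screening.

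The time origin is a separate matter. The infusion starts about 2 h before reperfusion, hence before ICU admission, so the two documents give different clocks for the same samples.

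**Working it through.** The plan states no figure on this point, so there is none to reproduce. The check compares the texts and adds simple arithmetic.

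**1. Where each measure is summarized by arm**

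| Measure | Screening | 12, 24, 36 h | Discharge |
|---|---|---|---|
| CLcr | no | no | no |
| Urine output | not applicable | no | not applicable |
| Bilirubin, ALT, AST | yes | no | yes |
| Serum creatinine | yes | no | yes |

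Planned results outside every by-arm table: CLcr, bilirubin, ALT and AST at 3 times, plus 3 urine-output periods, is 4 × 3 + 3 = 15 per patient, or 15 × 50 = 750 per arm. This counts data, not harm.

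**2. What other outputs would show of a protocol-mandated stop**

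- *Withdrawal tables (SAP 9.6.2, 9.6.3).* These need not show it, because "Patients who discontinue the treatment with the Investigational Product will not be withdrawn from the study by default".
- *Exposure (SAP 9.6.1, Table 3.1).* One stop at 24 h in an arm of 50 lowers mean duration by (48 − 24)/50 = 0.48 h; one stop at 36 h lowers it by (48 − 36)/50 = 0.24 h. SAP 9.1 also reports median, minimum and maximum. A single stop at 24 h pulls the minimum to 24 h or less, so the table can show that an early stop occurred. The median responds only if many patients stop. The table gives neither the number of stops nor the reasons.
- *Per-protocol exclusions (SAP 6.2 and 9.3, Table 1.3).* Less than 24 h of infusion excludes a patient. A hepatic stop on the 12 h test (drawn at 8–16 h) would therefore be counted by arm. The renal rule needs two consecutive points, the earliest being 12 and 24 h, so it is met at 24 h nominally, or 20–28 h with the window. A renal stop will usually miss this exclusion.
- *Listing 2.5.2.* Covers infusion termination, patient by patient.
- *AE tables (SAP 9.6.2).* An abnormal laboratory finding can be an AE (protocol 8.1.1), so they show whatever the investigator reports.

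**3. Precision of the missing table**

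Exact (Clopper–Pearson) 95% intervals with 50 per arm, for assumed counts: 0/50 gives 0–7.1%; 1/50 gives 0.1–10.6%; 5/50 gives 3.3–21.8%.

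**4. Time origin**

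The documents do not give the gap g from infusion start to ICU admission. If ICU admission is 0–6 h after reperfusion (an assumption that borrows the 6 h limit for T0 in Appendix 1), then g = 2 + (0 to 6) = 2–8 h, and longer when a second lung is reperfused later. The range shown is 2–10 h. A time t after ICU admission is t + g after infusion start:

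| Gap g | 12 h | 24 h | 36 h |
|---|---|---|---|
| 2 h | 14 | 26 | 38 |
| 4 h | 16 | 28 | 40 |
| 8 h | 20 | 32 | 44 |
| 10 h | 22 | 34 | 46 |
| Appendix 6 window | 8–16 | 20–28 | 32–40 |

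Once g exceeds 4 h, all three SAP times lie outside the protocol windows. Equally, a sample taken exactly on the protocol's schedule would look out of window on the SAP's clock. This has an effect only if someone assigns results to time points, which the SAP does not currently plan.

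**The case against.** The strongest reply is that listing these results is a deliberate choice that the protocol permits. A reader might infer that the SAP dropped a planned analysis. The documents do not support that: protocol 4.2.4 does not name the tests at 12, 24 and 36 h as a safety endpoint, section 9.4.6 plans no summary of them, and section 2.4.3.4 describes them as checks on whether treatment can continue. This part of the reply stands.

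A reader might also infer that nothing about on-infusion organ function reaches a by-arm output. That is too strong as well. The AE tables, the minimum in the exposure table and Table 1.3 each carry part of the information, and with about 100 patients counts can be recovered from the listings. What remains is that none of these outputs reports the test results themselves, or how many patients in each arm met the stopping criteria. The DMC reviews relevant available laboratory results (protocol 8.5), but that is oversight during the trial and not a summary in the study report.

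The sentence before the SAP's listing statement names only CLcr. For urine output and the hepatic tests, the listing-only status follows from Listing 4.15.5 and the absence of any table. That is an inference, but the output list leaves little room for another reading.

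On timing, a reader might infer that samples were to be drawn at the wrong hours. They were not: sites follow the protocol. The SAP wording matches the flow chart's column heading, which footnote 2 overrides for these tests.

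**Conclusion.** The point holds as a minor gap shared by both documents, plus a wording error in the SAP. The only scheduled on-infusion laboratory safety results, on which the protocol bases its stopping rule, have no by-arm summary. A transient difference between arms could pass through the laboratory tables unseen. By-arm information is partial, not absent, and the protocol is not breached.

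The effect on the trial's conclusions cannot be sized, because the documents give no rate of renal or hepatic dysfunction during infusion. Nothing here shows that harm occurred or would be concealed. The intervals rest on assumed counts, and the time shifts on an assumed gap of 2–10 h.

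The time origin is a true conflict between the documents, despite the statement in SAP 1.2. As the plan stands it changes no sampling and no summary, but it must be corrected before these tests are tabulated by time point.

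**What to change.** In SAP 9.6.4:

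1. Change the time origin from ICU admission to the start of study drug infusion.
2. Replace the listing-only statement with one descriptive by-arm table in the Safety population, containing:
   - CLcr, bilirubin, ALT and AST at screening and at 12, 24 and 36 h, with the number of patients with results at each time;
   - urine output for 0–12, 12–24 and 24–36 h, with the number of patients with results;
   - the number of patients exceeding the hepatic limits of protocol 6.3.2;
   - the number meeting the full renal criterion, with both components at two consecutive time points. If CLcr below 60 mL/min alone is also shown, label it as not being the stopping criterion.

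Leave the discharge and shift tables as they are. SAP 1.1 has the plan finalized before database lock, and SAP 8.2 places unblinding after lock, so the change can be pre-specified.

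The cost is one paragraph and a little programming on data already collected. The results would be descriptive, with wide intervals at about 50 per arm, and the table would not show dysfunction that begins after the 36 h test.

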#### 9.6.5 Concomitant Medications

All medications reported in the CRF as being taken prior to the Month 1 visit, categorized by medication group and subgroup according to WHO DRUG, will be summarized. The number and percentage of patients using at least one medication within each medication group and subgroup will be presented.

#### 9.6.6 Vital Signs, Physical Findings and Other Observations Related to Safety

##### Vital signs

Vital signs, including systolic and diastolic blood pressure and heart rate, are measured at Screening, ICU admission, every 12 hours post ICU admission until 120 hours post ICU admission or until ICU discharge or PA catheter removed whichever occurs earliest. Summary statistics for each of these three parameters will be presented by treatment group at each time point. Summary statistics for the change from screening to each post-screening time point will also be presented.

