4.2.4. Safety endpoints

- AE recording.
- Standard laboratory tests including hematology (hematocrit, hemoglobin, red blood cells, platelets, white blood cells, differential white blood cells count), and clinical chemistry (sodium, chloride, potassium, bicarbonate, serum creatinine, blood urea nitrogen, total bilirubin, alanine aminotransferase (ALT), aspartate aminotransferase (AST), prothrombin time or international normalized ratio, partial thromboplastin time). Laboratory tests will be performed at screening and at hospital discharge.
- Vital signs, i.e. blood pressure (BP) and heart rate (HR), assessed at screening, on ICU admission, and then q12 hours up to ICU discharge or up to 5 days after ICU admission, whichever occurs earlier.
- Cardiopulmonary physiologic measurements, including cardiac output (CO), pulmonary artery pressure (PA pressure), systemic vascular resistance (SVR), pulmonary vascular resistance (PVR), pulmonary capillary wedge pressure (PCWP), right atrial pressure (CVP). Assessment will be performed on ICU admission, and then q12 hours when PA catheter is present, up to ICU discharge or up to 5 days after ICU admission, whichever occurs earlier. Additional cardiopulmonary data obtained as per center standard of care will be collected in patients with clinical diagnosis of PGD up to the clinical recovery of the condition.

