7.5.2. Assessment in the ICU

The following will be assessed during ICU stay and recorded in the CRF, apart from SVR and PVR which will be calculated during data-management. Measurement will be performed as per center practice, unless otherwise specified. For the purpose of this study, clinically diagnosed PGD is defined as:

- An episode of decreased $\text{PaO}_2/\text{FiO}_2$ ratio and chest X-ray results consistent with a PGD score of grade 3, which is not the result of some other secondary cause of graft dysfunction [Christie, 2005]. When diagnosed, the condition is considered clinically recovered for a PGD score of ≤ 1 .
- $\text{PaO}_2/\text{FiO}_2$ ratio. $\text{PaO}_2/\text{FiO}_2$ ratio will be measured at $\text{FiO}_2 = 1$ q24 hours, up to extubation or up to 72 hours after ICU admission, whichever occurs earlier. Patients on $\text{FiO}_2 < 1$ will be turned back to $\text{FiO}_2 = 1$ for 5 minutes before gas measurement. Additional $\text{PaO}_2/\text{FiO}_2$ ratio values obtained as per center standard of care in patients with clinical diagnosis of PGD will be recorded in the CRF up to the clinical recovery of the condition.
- Chest X-rays. A chest X-rays will be obtained 24 hours, 48 hours, and 72 hours after ICU admission (see Appendix 1 for details).
- BP, HR. Vital signs will be measured q12 hours up to ICU discharge or up to 5 days after ICU admission, whichever occurs earlier.
- CO, PA pressure, SVR, PVR, PCWP, CVP. Cardiopulmonary physiologic measurements will be assessed q12 hours when a PA catheter is present, up to ICU discharge or up to 5 days after ICU admission, whichever occurs earlier. Additional measurements obtained as per standard of care in patients with clinical diagnosis of PGD will be recorded in the CRF up to the clinical recovery of the condition.

For all measurements above, the actual date and time of assessment will be recorded in the CRF.

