14.4. APPENDIX 4 - STUDY FLOW CHART

Test/Examination	Screening	Tx	ICU admission	Time after ICU admission							ICU discharge	Hospital discharge	1 month	6 months	12 months
				12 h	24 h	36 h	48 h	54 h	60 h	72 h					
Informed consent	X														
Inclusion/exclusion criteria ¹	X														
Laboratory tests	X										X				
Renal/hepatic function ²	X			X ²	X ²	X ³									
Study drug administration ³		X					X ²								
Pharmacokinetic sampling ²					X ²		X ²	X ²							
PaO ₂ /FiO ₂ ratio			X		X		X			X					
Chest X-ray			X		X		X			X					
Vital signs (BP & HR) ⁴	X		X	X	X	X	X		X	X	X				
Cardiopulmonary measurements ⁴			X	X	X	X	X		X	X	X				
BAL ⁵				X ⁵											
Vital status										X	X	X	X	X	
FEV ₁ & FVC												X	X	X	
BOS score													X	X	
Cumulative acute rejection													X	X	
Adverse Events ⁶		X										X ⁶	X	X	X ⁶
Prior and concomitant medications ⁷	X											X ⁷	X	X	X ⁷

1 = Confirmatory screening to take place upon admission to the center prior to randomization

2 = (shadowed boxes) Time is from the start of study drug infusion. The '24 hours' sample is taken @ 24±6 hours; the '54 hours' sample is taken in the interval 2-6 hours after the infusion end

3 = Study drug infusion will start approximately 2 hours before the anticipated time of reperfusion

4 = Vital signs and cardiopulmonary measurements (when a PA catheter is present) will be measured up to ICU discharge or up to 5 days after ICU admission, whichever occurs earlier

5 = BAL will be performed during mechanical ventilation, in the interval between 12 and 24 hours after reperfusion

6 = All AEs will be reported up to 10 days or hospital discharge. Thereafter, only untoward events that the Investigator assesses as at least possibly related to the study drug will be recorded

7 = After 10 days or hospital discharge, only drugs used for immunosuppression, infection prophylaxis, and AEs possibly related to the study drug (see 6 above) will be recorded

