## 3 STUDY DESIGN

### 3.1 Overview

This is a phase 2, multi-center, randomized, double blind, placebo-controlled, parallel group study of repertaxin in the prevention of PGD after lung transplantation. The study will involve 100

patients undergoing single or bilateral lung transplant who will be randomized to receive either repertaxin or placebo via continuous intravenous (i.v.) infusion administered over 48 hours. Patients randomized into the study who do not go on to receive study drug or lung transplant will be replaced therefore the total number of patients randomized may exceed 100. Patients will be followed for 12 months post-transplant but the majority of study assessments are performed during the intensive care unit (ICU) and hospital stay immediately after surgery.

Patients will be selected for entry into the study from those listed on the center's lung transplant waiting list. Inclusion/exclusion criteria (as listed in protocol sections 5.1 and 5.2), disease history, extrapulmonary site of infection, significant medical history, vital signs, renal and hepatic function, laboratory safety tests and donor information will all be assessed prior to randomization to ensure patient eligibility.

The lung transplant surgery will be performed according to the center's standard practice. The study drug infusion will start approximately 2 hours before the anticipated time of reperfusion of the first allograft. A loading dose will be administered for the first 30 minutes, followed by a maintenance dose for the remaining 47.5 hours of administration.

After completion of surgery, patients will be admitted to an ICU and blood gases ( $\text{PaO}_2$ ,  $\text{FiO}_2$  and  $\text{PaO}_2/\text{FiO}_2$  ratio) will be measured on admission (time 0) and at 24, 48 and 72 hours post ICU admission or until extubation whichever occurs earlier. Chest x-rays, renal and hepatic function and PK sampling will be measured at defined time points within the 72 hours following ICU admission. Vital signs (BP and HR) and cardiopulmonary measurements will be assessed at defined time points within the 5 days post ICU admission or until ICU discharge (or PA catheter removed) whichever occurs earlier. Further patient assessments are made at ICU discharge and hospital discharge.

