##### Cardiopulmonary measurements

Cardiopulmonary measurements consist of CVP, PCWP, CO and PA Pressure (systolic/diastolic) and are measured at ICU admission, every 12 hours post ICU admission until 120 hours post ICU admission or until ICU discharge or PA catheter removed whichever occurs earliest. These data will be summarized by treatment group at each time point. Summary statistics for the derived variables SVR and PVR (see Section 5 for definitions) will also be provided.

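### SAP 9.6.6 ends blood pressure and heart rate at PA-catheter removal, a limit the protocol sets only for cardiopulmonary measurements; read literally, it would drop later readings from the by-arm safety tables

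*SAP*

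**What the plan says.** **Protocol.** Section 4.2.4 lists blood pressure and heart rate as safety endpoints, "assessed at screening, on ICU admission, and then q12 hours up to ICU discharge or up to 5 days after ICU admission, whichever occurs earlier". Section 7.5.2 gives the same stop: "Vital signs will be measured q12 hours up to ICU discharge or up to 5 days after ICU admission, whichever occurs earlier". The synopsis agrees. None of the three mentions a catheter for these two variables. The catheter appears in the separate item for cardiac output, PA pressure, the two vascular resistances, wedge pressure and right atrial pressure: "Cardiopulmonary physiologic measurements will be assessed q12 hours when a PA catheter is present".

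**SAP.** Section 9.6.6, under vital signs, sets the times as "every 12 hours post ICU admission until 120 hours post ICU admission or until ICU discharge or PA catheter removed whichever occurs earliest". The next paragraph, on cardiopulmonary measurements, ends with the same stopping phrase. Section 3.1 covers both sets of measurements in one sentence, "within the 5 days post ICU admission or until ICU discharge (or PA catheter removed) whichever occurs earlier". Section 1.2 reports no changes from the protocol.

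**The concern.** A cuff or arterial-line pressure and a heart rate do not depend on a PA catheter, and the protocol does not make them depend on one. The SAP's vital-signs sentence looks as if it took over the stop that belongs to the cardiopulmonary paragraph.

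Blood pressure and heart rate are repeated safety readings during and just after a 48-hour infusion of an investigational drug. Protocol 9.4.6 promises summaries at each time point and changes from screening. If the tables follow the SAP sentence, a patient who is still in the ICU leaves the vital-signs summary when the catheter comes out. That is a post-randomization event, and the protocol gives it no role for these variables. Both the raw summaries and the changes from screening would be affected.

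**Working it through.** No sample size, power or alpha figure is involved, so there is no stated number to reproduce. The check is a comparison of texts and a count of scheduled readings.

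**1. Stopping rules side by side**

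| Place | Blood pressure, heart rate | Cardiopulmonary set |
|---|---|---|
| Protocol synopsis, 4.2.4, 7.5.2 | Earlier of ICU discharge or 5 days | Same, while a PA catheter is present |
| Protocol Appendix 4, footnote 4 | One footnote for both rows; the catheter parenthesis follows the cardiopulmonary term | Catheter condition applies |
| SAP 3.1 | One joint sentence, catheter removal in parentheses; ambiguous | Same sentence |
| SAP 9.6.6 | Earliest of 120 h, ICU discharge or catheter removal | Same phrase |

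Five days is 120 h, so that limit agrees. The only difference for blood pressure and heart rate is the catheter clause. It is unambiguous in SAP 9.6.6, because the vital signs have their own paragraph there.

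**2. Can it reach the tables?** The SAP sentence describes when the signs are measured and orders no deletion. The sentence after it says "Summary statistics for each of these three parameters will be presented by treatment group at each time point". However, SAP 9.6.6 is the analysis text that defines which vital-sign time points exist, and SAP 10 checks outputs against the plan's specifications. One programmer could cut at catheter removal, citing the SAP. Another could keep every reading, citing the protocol.

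**3. Count of scheduled readings.** Take a patient in the ICU for the full 120 h, with readings every 12 h from ICU admission:

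- Protocol rule: 120/12 + 1 = 11 post-screening readings.
- SAP rule read literally, catheter removed at r hours, with the reading at r kept: r/12 + 1 readings.

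| Assumed removal | Kept | Dropped |
|---|---|---|
| 24 h | 24/12 + 1 = 3 | 8 |
| 48 h | 48/12 + 1 = 5 | 6 |
| 72 h | 72/12 + 1 = 7 | 4 |
| 96 h | 96/12 + 1 = 9 | 2 |

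The removal times are assumptions; the documents give none.

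**4. Could a dropped reading be on drug?** Let d be the hours from start of infusion to ICU admission. The 48 h infusion then ends 48 − d hours after ICU admission. The 36 h reading falls within it if 36 ≤ 48 − d, that is, if d ≤ 12. The documents do not give d. For an assumed d of 4 to 8 h, the infusion ends 44 to 40 h after ICU admission, so removal at 24 h would also drop one on-drug reading, the one at 36 h.

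**The case against.** The strongest reply is that this is loose wording with no certain effect. Much of that reply stands:

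- **Lost data.** A reader might infer that readings are lost. The documents do not support that. The protocol governs collection, SAP 1.1 says the SAP is to be read together with it, SAP 9.1 lists all CRF data, and Listing 4.17.1 covers vital signs. What is at risk is inclusion in the by-arm summaries.
- **Sicker patients.** A reader might infer that later means would describe the sicker patients. No document gives removal times or links removal to severity. The protocol's own stop at ICU discharge already restricts later time points by a post-randomization clinical decision. The catheter clause could only add to that selection, by an unknown amount.
- **Patients without a catheter.** A reader might think they have no defined window. They do: under an earliest-of rule, a removal that never happens cannot be the earliest event, so they keep the full protocol window.
- **SAP 3.1.** Its joint sentence can be read as limiting only the catheter measurements. The protocol's own footnote is similar: "Vital signs and cardiopulmonary measurements (when a PA catheter is present) will be measured up to ICU discharge or up to 5 days". SAP 3.1 is therefore weak evidence of a second error.
- **Importance.** These are descriptive tables with no test, and adverse events are recorded whatever the catheter status.

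The reply does not remove the contradiction in the vital-signs paragraph of SAP 9.6.6. By-patient listings do not replace a summary by arm, and a check of outputs against the plan would not catch an error that is in the plan.

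**Conclusion.** The concern holds as an undeclared inconsistency between the SAP and the protocol in the definition of a safety endpoint. SAP 9.6.6 gives blood pressure and heart rate a stopping rule that Protocol 4.2.4 and 7.5.2 do not. If it is programmed literally, later summaries would omit patients who are still in the ICU and whose readings the protocol requires.

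The size cannot be computed. Per patient with a full 120 h stay, the illustration is 2 to 8 of 11 readings omitted for assumed removal between 96 h and 24 h; shorter ICU stays have fewer readings to lose. The conclusion rests on a literal reading of the sentence, which the plan permits but does not compel. The primary analysis and the other efficacy analyses are unaffected.

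**What to change.** 1. In the vital-signs paragraph of SAP 9.6.6, delete the catheter-removal clause and state that all blood pressure and heart rate readings up to ICU discharge or 120 h, whichever is earlier, are summarised.
2. In SAP 3.1, reword the joint sentence so that the catheter condition applies only to the cardiopulmonary measurements.
3. Leave the cardiopulmonary paragraph of SAP 9.6.6 as it is.

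No extra provision is needed for the number of patients at each time point, because SAP 9.1 already includes it among the standard summary statistics. The cost is two wording edits before the SAP is finalized ahead of database lock. No new data are needed, since the protocol already requires these readings, and the edits make the statement in SAP 1.2 true on this point.
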